5.3 Eligibility Criteria

5.3.1 General Eligibility Criteria

Assessment for general eligibility criteria is based on medical records of the site and interview with a candidate patient. Patients must meet ALL general inclusion criteria to participate in the clinical investigation. If ANY general exclusion criteria are met, the patient is excluded from the clinical investigation and cannot be enrolled (recruitment or screen failure depending on whether or not the patient has signed the Informed consent [screen failure]).

If any clinical and/or laboratory tests are required for patient screening and are not included in a site's standard tests, they must be completed after written informed consent is obtained.

Template: 86357 Rev. J Page **17** of **61**

5.3.2 Inclusion Criteria

- 1. Subject is willing and able to provide written informed consent prior to any clinical investigation-related procedure.
- 2. Subject is implanted with the CardioMEMS PA Sensor for a minimum of 3 months at time of consent.
- 3. Subject is ≥ 18 years of age.
- 4. Subject is willing and able to undergo several cardiac MRI scans. This is including but not limited to:
 - Subject must have all MRI compatible devices
 - Subject must be able to hold their breath during imaging
 - Subject must be free of all metal bodies, fragments, or implants that would prohibit MRI imaging
- 5. Subject is willing and able to upload PA pressure information (i.e., take daily CardioMEMS readings and have their hemodynamic information collected at study visits) and comply with the follow-up requirements.

5.3.3 Exclusion Criteria

- 1. Subject will receive or is likely to receive an advanced therapy (e.g., mechanical circulatory support or cardiac transplant) in the next 6 months.
- 2. Subject was implanted with Cardiac Resynchronization Therapy (CRT)-Pacemaker (CRT-P) or CRT-Defibrillator (CRT-D) for less than 90 days prior to consent.
- 3. Subject is pregnant or planning to become pregnant in the next 6 months.
- 4. Subject is enrolled into another trial with an active treatment arm.
- 5. Subject has significant congenital heart disease that has not been repaired.
- 6. Subject is implanted with mechanical right heart valve(s).
- 7. Subject has unrepaired severe valvular disease.
- 8. Subject has an anticipated life expectancy of < 6 months.
- 9. Subject has an active, ongoing infection, defined as being febrile, an elevated white blood cell count, on intravenous antibiotics, and/or positive cultures (blood, sputum, or urine).
- 10. Subject has had a major cardiovascular event (e.g., unstable angina, myocardial infarction, percutaneous coronary intervention, open heart surgery, or stroke, etc.) within 90 days prior to consent.
- 11. Subject has any condition that, in the opinion of the Investigator, would not allow for utilization of the CardioMEMS HF System to manage the subject using information gained from hemodynamic measurements to adjust medications, including the presence of unexpectedly severe pulmonary hypertension (e.g., trans-pulmonary gradient >15) at implant RHC, a history of non-compliance, or any condition that would preclude ability to obtain CardioMEMS PA Sensor readings and paired cardiac MRI data from being collected.
- 12. Subjects who, in the opinion of the investigator, are at-risk for serious adverse reaction to Dobutamine (ex. subjects with idiopathic hypertrophic subaortic stenosis and subjects who have shown previous manifestations of hypersensitivity to Dobutamine) should be excluded from the study.

Sites should instruct female patients of childbearing potential to use safe contraception (e.g., hormonal contraceptives: contraceptive pills, implants, transdermal patches hormonal vaginal devices, injections with prolonged release.) It is accepted, in certain cases, to include subjects having a sterilized regular

Template: 86357 Rev. J Page **18** of **61**

partner or subjects using a double barrier contraceptive method. However, this should be explicitly justified in special circumstances arising from the clinical investigation design, product characteristics and/or clinical investigation population.

5.4 Subject Enrollment

A patient is considered enrolled in the clinical investigation only when they have met all inclusion and no exclusion criteria and have provided written informed consent. If subjects enter the study without meeting all the items listed above, they should complete all follow-up requirements. These subjects are considered CIP deviations.

5.4.1 Enrollment of Medicare Beneficiaries

This clinical investigation will enroll Medicare beneficiaries and therefore conforms to all standards of Medicare coverage requirements. The Risks and Benefits section describes how all enrolled subjects, including Medicare beneficiaries, may be affected by the device under investigation. Subjects enrolled in the clinical investigation are expected to be consistent with the Medicare population based on age and as such, the clinical investigation results are expected to be generalizable to the Medicare population.

5.4.2 Historically Under-Represented Demographic Subgroups

The Sponsor intends to implement FDA's guidance on sex-specific data in medical device clinical investigations to ensure adequate representation of women and other traditionally under-represented demographic subgroups in this clinical investigation. As noted in the guidance, some barriers to participation of women and ethnic minorities in clinical investigations have traditionally been:

- Lack of understanding about main obstacles to participation of such subgroups in clinical research
- Inclusion/exclusion criteria potentially not needed to define the clinical investigation population may unintentionally exclude specific subgroups
- Under diagnosis of disease etiologies and pathophysiology leading to under referral of demographic subgroups
- Avoidance of specific subgroups by investigators and Sponsor due to the perception that it takes more time and resources to recruit them
- Fear of fetal consequences (for female participants)
- Family responsibilities limiting women's ability to commit time for follow-up requirements

The Sponsor will take the following steps to ensure adequate representation of women and racial or ethnic minorities in this clinical investigation:

- The Sponsor will provide training to investigational site personnel to ensure adequate representation of these demographic subgroups
- The Sponsor will regularly review enrollment data to investigate whether there is underrepresentation of these demographic subgroups
- As appropriate and necessary, the Sponsor will retrain sites on the importance of recruiting and retaining subjects in the clinical investigation
- The Sponsor will approach sites without bias or consideration for specific demographic subgroups

Template: 86357 Rev. J Page **19** of **61**

5.5 Subject Withdrawal and Discontinuation

Each subject meeting all general and screening eligibility criteria shall remain in the clinical investigation until completion of the required follow-up period; however, a subject's participation in any clinical investigation is voluntary and the subject has the right to withdraw at any time without penalty or loss of benefit. Conceivable reasons for discontinuation may include, but not be limited to, the following:

- Subject death
- Subject voluntary withdrawal
- Subject lost-to follow-up as described below
- Subject's follow-up is terminated due to subject non-compliance.

Sites must notify the Sponsor of the reason(s) for subject discontinuation. Investigators must also report this to their respective IRB as defined by their institution's procedure(s).

No additional follow-up is required, or data recorded from subjects once withdrawn from the clinical investigation, except for the status (deceased/alive).

However, if a subject withdraws from the investigation due to problems related to the safety or performance of the device under investigation, the investigator shall ask for the subject's permission to follow his/her status/condition outside of the clinical investigation.

In case of subject withdrawal of consent, the site should make attempts to schedule the subject for a final clinical investigation visit. At this final follow-up visit, the following will be recorded, with the subject's permission:

- Subject status (deceased/alive)
- · Any adverse event details prior to withdrawal of consent

Lost-to-Follow-up

If the subject misses two consecutive scheduled follow-up time points and the attempts at contacting the subject detailed below are unsuccessful, then the subject is considered lost-to-follow-up. Site personnel shall make all reasonable efforts to locate and communicate with the subject (and document these efforts in the source documents), including the following, at each contact time point:

- A minimum of two telephone calls on different days over the specified follow-up windows to contact the subject should be recorded in the source documentation, including date, time, and initials of site personnel trying to make contact.
- If these attempts are unsuccessful, the site should send a letter (certified if applicable) to the subject.
- If a subject misses one or more non-consecutive follow-up contact time points, it will be
 considered a missed visit. The subject may then return for subsequent visits. If the subject misses
 two consecutive time points and the above-mentioned attempts at communicating with the
 subject are unsuccessful, the subject will be considered lost-to-follow-up.

Note: Telephone contact with General Practitioner, non-clinical investigation cardiologist, or relative without the presence of the subject or indirect documentation obtained via discharge letters will not be considered as subject contact.

Template: 86357 Rev. J Page **20** of **61**

5.6 Number of Subjects

5.7 Total Expected Duration of the Clinical Investigation

The expected duration of each subject's participation is 3 months, including the scheduled visits and data collection for this clinical investigation that will occur at baseline and 3 months. Subjects will exit the trial at the end of their 3-month follow-up visit.

6.0 TREATMENT AND EVALUATION OF ENDPOINTS

The Principal Investigator is responsible for ensuring all clinical trial data are collected as required per this CIP. Trained Sponsor personnel may provide technical expertise and technical guidance on the use of the CardioMEMS HF System, including the Merlin.net website.

6.1 Screening Procedures

The following information will be evaluated from medical records and documented, to ensure each subject meets entry criteria.

- Subject is implanted with the CardioMEMS PA Sensor for a minimum of 3 months at time of consent.
- Age ≥ 18 years
- Subject has not been implanted with Cardiac Resynchronization Therapy (CRT)-Pacemaker (CRT-P) or CRT-Defibrillator (CRT-D) for less than 90 days prior to consent
- Subject has not had a major cardiovascular event (e.g., unstable angina, myocardial infarction, percutaneous coronary intervention, open heart surgery, or stroke, etc.) within 90 days prior to consent
- Cardiovascular history including:
 - o previous cardiac procedures and CRT device information
 - o relevant co-morbidities

to ensure subjects will meet imaging inclusion and exclusion criteria.

Enrollment Assessments

The following assessments and information will be collected during the Enrollment visit:

Template: 86357 Rev. J Page 21 of 61

- Patient & Investigator signed Informed Consent
- Verification of inclusion and exclusion criteria (as necessary from the screening procedures).

Once a duly dated and signed Informed Consent form is obtained, sites will confirm the patient meets all inclusion criteria and does not meet any of the exclusion criteria. A patient is considered enrolled in the clinical investigation only when they have met all inclusion and no exclusion criteria and have provided written informed consent.

6.1.1 Screening Failure

If a consented subject does not meet all inclusion criteria or meets any of the exclusion criteria, the subject is considered a screening failure. The Principal Investigator or the delegated trial personnel will record the screening failure in the subject's records and on a screening log as required. To assist the Sponsor in understanding reasons for screening failure, a screening log must be maintained and submitted to the Sponsor on a regular basis. If appropriate, subjects who fail screening may be rescreened at a later date. If any subject discontinues participation after informed consent has been obtained, but prior to any study visit procedures are conducted, the subject must be also documented as a screening failure.

6.1.2 Baseline Assessments

The following assessments and information will be collected during the baseline visit prior to imaging (see Table 2 for additional details).

- Documentation of key demographic information such as ethnicity, sex at birth, and age
- Subject medical history and co-morbidities
- Physical exam including vital signs
- Cardiovascular history including:
 - o previous cardiac procedures and CRT device information
 - o relevant co-morbidities
 - HF assessment including NYHA class evaluation
- HF medication review with documentation
- Limited echo to document EF
- NYHA class evaluation within the previous 30 days
- Calculation of BMI using subject height and weight (see Appendix III) and calculation of chest circumference measurement if BMI > 35kg/m²

[figure not shown]
It is strongly recommended that the site obtain alternate contact information for the subject in the event the subject cannot be reached or does not attend follow-up visits. Sites will be encouraged to include the subject's family or significant others in the consent process as well as trial education efforts. This information should be maintained in the subject's research chart.

6.1.3 Baseline Imaging Assessments

[figure not shown]
Template: 86357 Rev. J Page 22 of 61

Template: 86357 Rev. J Page 23 of 61

6.1.4 Baseline CIP-Required Medication

Template: 86357 Rev. J Page 24 of 61

6.2 Blinding

Investigators and subjects will not be blinded.

6.3 Follow-up Assessments

Subjects will have one follow-up visit at 3 months after the baseline visit has occurred.

The following assessments and information will be collected during the follow-up visit prior to imaging (see Table below for additional details).

- · Physical exam including vital signs
- Changes to cardiovascular history including:
 - o previous cardiac procedures and CRT device information
 - o relevant co-morbidities
- HF assessment including NYHA class evaluation
- HF medication review with documentation
- · Limited echo to document EF
- NYHA class evaluation within the previous 30 days
- Calculation of BMI using subject height and weight (see Appendix III) and calculation of chest circumference measurement if BMI > 35kg/m²

6.3.1 Follow-up Imaging Assessments

6.3.2 Follow-up CIP-Required Medication

Template: 86357 Rev. J Page 25 of 61

6.3.3 Schedule of Events

| CIP Activity | Enrollment/ Baseline | 3 Month ((± 7 days) |
|----------------------------------|-------------------------|------------------------|
| Informed Consent Process | X | |
| Demographics | Χ | |
| Physical Examination | Х | Χ |
| Cardiovascular History | Χ | |
| Medical History | X | |
| Medication | X | Χ |
| EF Assessment (Echo) | Χ | Χ |
| NYHA Assessment | Χ | Χ |
| cMRI | X | Χ |
| CardioMEMS HF System Readings | X | X |
| Adverse Event | As Occurs | As Occurs |
| Deviation | As Occurs | As Occurs |
| Non-AE Device Issue | As Occurs | As Occurs |
| Withdrawal | As Occurs | As Occurs |
| Death | As Occurs | As Occurs |

6.4 Requirement for Clinical Laboratories

A core lab will be employed to train imaging personnel, collect images and imaging data, review and assess images and imaging data (via an independent reviewer), and store images and imaging data.

7.0 ADVERSE EVENTS

To comply with worldwide standards and guidelines on clinical investigation adverse event reporting, the Sponsor has adopted uniform and worldwide applicable standard definitions and reporting timelines to be used and adhered to by the investigators.

7.1 Definition

7.1.1 Adverse Event

An adverse event (AE) is any untoward medical occurrence, unintended disease or injury, or untoward clinical signs (including abnormal laboratory findings) in subjects, users, or other persons, whether or not related to the medical device under investigation.

As part of ISO 14155 Section 3.2, the Adverse Event definition has the following notes:

Template: 86357 Rev. J Page **26** of **61**

Note 1: This definition includes events related to the medical device under investigation.

Note 2: This definition includes events related to the procedures involved.

Note 3: For users or other persons, this definition is restricted to events related to medical devices under investigation.

7.1.2 Serious Adverse Event

If the AE meets any of the criteria below, it is regarded as a serious adverse event (SAE).

- a) Led to a death,
- b) Led to a serious deterioration in health of the subject, that either resulted in
 - 1. a life-threatening illness or injury, or
 - 2. a permanent impairment of a body structure or a body function, or
 - 3. in-patient hospitalization or prolongation of existing hospitalization, or
 - 4. medical or surgical intervention to prevent life threatening illness or injury or permanent impairment to a body structure or a body function.
 - 5. chronic disease
- c) Led to fetal distress, fetal death or a congenital abnormality or birth defect.

Note: A planned hospitalization for a pre-existing condition, or a procedure required by the CIP without a serious deterioration in health, is not considered to be an SAE.

7.1.3 Device Deficiency/Device Malfunction

Device deficiency is defined as an inadequacy of a medical device related to its identity, quality, durability, reliability, safety, or performance, such as malfunction, misuse or use error and inadequate labeling. This includes the failure of the device to meet its performance specifications or otherwise perform as intended. Note: performance specifications include all claims made in the labeling of the device.

A device malfunction is the failure of a device to meet its performance specifications or otherwise perform as intended, when used in accordance with the instructions for use or CIP.

7.2 Device Relationship

Determination of whether there is a reasonable possibility that an investigational product or device under investigation caused or contributed to an AE is to be **determined by the Investigator** and recorded on the appropriate Case Report Form (CRF). Determination should be based on the assessment of temporal relationships, evidence of alternative etiology, medical/biologic plausibility, and patient condition (pre-existing condition).

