2.2 Devices Used in the Clinical Investigation

2.2.1 Name of the Devices Under Investigation

Table 1 details the devices to be used in this study. The CardioMEMS HF System is currently approved by FDA in the US (P100045) and available for market release. The algorithm/software used to estimate CO will be considered investigational in this study.

Table 1: Identification of Devices under Investigation

| Device name | Model | Manufacturer | Region/ Country | Investigational or Market Released |
|---|------------------|--|-----------------|---------------------------------------|
| CardioMEMS™ PA Sensor and Delivery System | CM2000 | St. Jude Medical, an Abbott Company | United States | Market Released |
| CardioMEMS™ Hospital Electronics System | CM3000 CM3100 | St. Jude Medical, an Abbott Company | United States | Market Released |
| Merlin [™] Patient Care Network | CM6000 | St. Jude Medical, an Abbott Company | United States | Market Released |
| CardioMEMS Backend WebApp | CM4000 | St. Jude Medical, an Abbott Company | United States | Market Released |

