11.3 Source Documentation

Regulations and Good Clinical Practice (GCP) require the Investigator to maintain information in the subject's original medical records that corroborates data collected on the CRFs. To comply with these regulatory requirements/GCP, sites should include the following information in the subject record at a minimum and if applicable to the clinical investigation:

- Medical history/physical condition of the subject before involvement in the clinical investigation sufficient to verify CIP entry criteria
- Dated and signed notes on the day of entry into the clinical investigation referencing the Sponsor,
 CIP number, subject ID number, and a statement that informed consent was obtained
- Dated and signed notes from each subject visit (for specific results of procedures and exams)
- AEs reported and their resolution, including supporting documents, such as discharge summaries, catheterization laboratory reports, ECGs, and lab results including documentation of site awareness of SAEs and of investigator assessment of device relationship for SAEs.
- CIP-required laboratory reports and assessments, reviewed and annotated for clinical significance of out of range results (if applicable).
- Notes regarding CIP-required and prescription medications taken during the clinical investigation (including start and stop dates)
- Subject's condition upon completion of or withdrawal from the clinical investigation
- Any other data required to substantiate data entered into the CRF

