15.3 Risks Associated with Participation in this Clinical Investigation

As part of study participation, subjects will undergo a series of cMRI scans. As the CardioMEMS PA Sensor is non-ferrous and MRI conditional, there are no anticipated additional risks introduced to trial subjects due to cMRI. All risk mitigations associated with MRI use in conjunction with the CardioMEMS HF System are included in the Sensor Design FMEA (Reference: TR-1002-70, Rev. AA). Subjects will also be administered a study medication at each of the two study visits in order to modulate cardiac output. Possible protocol administered medication interactions are described below in section 15.4.

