15.6 Risk to Benefit Rationale

Congestive HF is a progressive disease and HF patients are generally symptomatic. Symptoms of dyspnea and fatigue increase with elevations of pressures within the heart and lungs, leading to instances of acute HF decompensation. The CardioMEMS HF System enables clinicians to medically manage HF patients by adjusting treatments to keep PA pressures within target ranges to prevent or reduce instances of acute HF decompensation. In doing so, the CHAMPION trial demonstrated a reduction in rates of HF decompensation resulting in an HFH, in NYHA Class III patients who had a HFH within the prior 12 months. In addition to pressure, CO is an important variable to describe hemodynamic pathophysiology in patients with HF. Deriving CO as part of remote monitoring with the CardioMEMS HF System is expected to produce an accurate assessment of CO without the associated risks and costs of traditional methods such as Fick and Thermodilution. CO monitoring using the CardioMEMS HF System can potentially provide important information to manage patients with HF. There are no new or additional risks related to the study device as part of the study protocol beyond the risks already incurred by the study subjects as they will already be implanted with the CardioMEMS PA Sensor and are currently using the CardioMEMS HF System. As part of study participation, subjects will undergo a series of cMRI scans. Since the CardioMEMS PA Sensor is non-ferrous and MRI conditional, there are no anticipated additional risks introduced to trial subjects due to cMRI. Subjects will also be administered a study medication to modulate CO. All precautions, including medical supervision during medication administration, will be taken to minimize any potential adverse effects from the medication administered per protocol. With the appropriate mitigations in place, the risks associated with participation in this study are outweighed by the potential benefit of providing CO via remote monitoring without the risks and costs associated with other CO assessments.

Template: 86357 Rev. J Page **40** of **61**

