3.2 Adverse Events

Adverse events are defined in Section 7.1 of the Clinical Investigational Plan. All adverse events will be summarized for all subjects in the Enrolled population as number and percentage of all subjects who experience the event and the total number of events.

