3.5 Descriptive Endpoints or Additional Data

Descriptive endpoints will evaluate data for the following data samples:

- 1) Baseline measurements recorded at rest
- 2) Baseline measurements recorded following introduction of Dobutamine
- 3) All Baseline measurements
- 4) 3 Month measurements recorded at rest
- 5) 3 Month measurements recorded following introduction of Dobutamine
- 6) All 3 Month measurements
- 7) Baseline and 3 Month measurements recorded at rest
- 8) Baseline and 3 Month measurements recorded following introduction of Dobutamine
- 9) All Baseline and 3 Month measurements

Statistical Analysis Plan

4.0 **DOCUMENTATION AND OHER CONSIDERATIONS**

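### Causality is required only against the investigational product or device, so the planned safety summary cannot separate harm from the study medication or the cMRI sessions

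*Protocol*

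**What the plan says.** Protocol 7.2 is the only causality instruction in the visible text. It gives the investigator "Determination of whether there is a reasonable possibility that an investigational product or device under investigation caused or contributed to an AE", to be recorded on the CRF. Protocol 11.3 lists what the subject record must hold for adverse events, including "documentation of site awareness of SAEs and of investigator assessment of device relationship for SAEs". It mentions no relationship to anything other than the device.

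On what is investigational, Protocol 2.2.1 states: "The algorithm/software used to estimate CO will be considered investigational in this study". The sensor itself is market released and was implanted before the study.

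On risk, Protocol 15.6 says: "There are no new or additional risks related to the study device as part of the study protocol". Protocol 15.3 names what is added. Subjects undergo a series of cMRI scans, and "Subjects will also be administered a study medication at each of the two study visits in order to modulate cardiac output". SAP 3.5 lists data samples such as "Baseline measurements recorded following introduction of Dobutamine", and exclusion criterion 12 concerns dobutamine reactions, so the study medication is evidently dobutamine.

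On analysis, SAP 3.2 says: "All adverse events will be summarized for all subjects in the Enrolled population as number and percentage of all subjects who experience the event". It adds the total number of events, and gives no breakdown by cause or by timing.

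**The concern.** The one causality judgment that is required is aimed at the exposure from which the protocol expects no new harm. The algorithm does not act on the patient, and the sensor was in place and in use before consent. The exposures that exist only because of the study are the drug given to change cardiac output and the scanning sessions. No relationship to either is asked for by name.

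An event provoked by the study medication could therefore be assessed as unrelated to the device and then enter the AE table with no mark that a study procedure caused it. Protocol 15.6 rests its risk-benefit conclusion partly on keeping adverse effects of the protocol-administered drug to a minimum. The planned safety summary would offer no direct way to check that.

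**Working it through.** There is no sample size, power or rate to reproduce here, so the check sets the sections side by side.

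1. **What must be attributed.** Protocol 7.2 names an investigational product or the device under investigation. Protocol 11.3 names device relationship, for SAEs. The derived categories are also device- or system-based: UADE in 7.2.1, and ADE, SADE and DSRC in Appendix II.

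2. **What the study adds.** Protocol 15.3 gives a series of cMRI scans and a study medication at each of two visits. Protocol 15.6 says the device adds nothing beyond existing implant and use. The sponsor treats the drug as a hazard worth managing: exclusion criterion 12 removes subjects at risk of a serious reaction to dobutamine, and 15.5 requires medical supervision of study-administered drugs.

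3. **What is collected and reported.** Protocol 7.1.1 defines an AE irrespective of device relationship, and its Note 2 includes procedure-related events. Under 7.3.1, sites report all AEs, and all SAEs go to the sponsor within 3 calendar days and on to the IRB. Under 7.3.4, the sponsor reports SAEs to the regulator per local requirements. Protocol 15.5 repeats that sites report all AEs. None of these duties depends on a device judgment.

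4. **What is tabulated.** SAP 3.2 counts subjects and events over the Enrolled population, with no relationship column.

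Steps 3 and 4 together locate the gap. Procedure-related events are brought in as AEs by definition, but no later section requires that relationship to be recorded, and no planned table shows it.

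5. **Scale.** Appendix VII allows up to 90 subjects, and 15.3 gives the drug at two visits. Counting one session per visit, 90 × 2 = 180. This is a ceiling: it assumes full enrolment and that every subject receives the medication at both visits. The documents give no adverse-event rate per session, so no event count follows.

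**The case against.** The strongest reply is that nothing is hidden. Every AE and SAE is reported whatever its cause, and procedure-related events are expressly AEs. A reader might infer from the device-only wording that harm from dobutamine or cMRI would go unreported. Protocol 7.1.1, 7.3.1, 7.3.4 and 15.5 contradict that, so this part of the reply stands in full.

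A reader might also infer that such harm could not be attributed at all. That too goes beyond the documents:

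- The term investigational product is undefined. Section 2.2.1 classifies the items in a device table and does not settle whether the term covers the study drug.
- Section 7.2 tells the investigator to weigh timing and other possible causes, so a drug effect has to be considered.
- Section 11.3 requires notes on CIP-required medications with start and stop dates, so timing can be traced at source.
- The CRF is not among the documents and may already carry drug or procedure fields.
- The bodies of 6.1.3, 6.1.4, 6.3.1, 6.3.2 and 15.4 are not shown in the public text. No omission can be inferred from them.

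These points limit the concern but do not remove it. Even if investigational product includes dobutamine, 7.2 poses one combined question that does not separate drug from device, and it still leaves out cMRI. Section 11.3 remains device only. A CRF field, if there is one, would have no stated requirement behind it in 7.2 or 11.3 and no planned table in SAP 3.2.

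It is also fair to say that the objectives concern algorithm development and agreement, and that the success criterion in SAP 2.7 makes no use of AE attribution.

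**Conclusion.** The point holds as a gap in attribution and tabulation, not in reporting. In the visible text, causality is required only for the investigational product or device, and the SAP does not split AEs by relationship. Harm from the study medication or cMRI therefore cannot be separated in the planned safety summary, and that summary cannot be used to check 15.6.

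Up to 180 study-drug sessions are affected. How many events that means is unknown, and any figure would rest on an assumed rate.

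The primary endpoint and the trial's success rule are untouched. This is a cheap improvement that should be made, not a threat to the validation result. It rests on the visible text of 7.2, 11.3 and SAP 3.2, and on dobutamine being the medication meant in 15.3. If the CRF already records these relationships, the gap narrows to protocol wording and one missing table.

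**What to change.** - **Protocol 7.2:** require the investigator to record relationship separately to (a) the device/algorithm, (b) the CIP-administered study medication and (c) the cMRI procedure, with onset relative to the study session. Add the same fields to the AE CRF if they are not already there.
- **Protocol 11.3:** extend the source-document item to match.
- **SAP 3.2:** add a table of AEs and SAEs by each relationship.

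The cost is a few CRF fields at most, two protocol text edits and one more table, with slightly more data entry at sites. No dose, schedule or clinical rule changes. The edits are best made before further sessions take place, because attribution is most reliable when recorded at the time of the event.
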